## **6.9.2 Secondary Endpoints**

### **6.9.2.1 ALT Remission**

All TTR and responder analyses described below will be repeated for both ALT normal range definitions:

- <20 U/L for women and <30 U/L for men
- <40 U/L

#### **Time to Remission**

TTR defined as the time in weeks from randomization to liver function remission, defined as two consecutive ALT values within normal range during the treatment period (i.e. excluding Week 28 follow-up visit), will be assessed by survival analysis. The time to the first of the two consecutive ALT values within normal range will be used for the TTR. The time in weeks will be calculated as (sample date – first dose date + 1)/7. For those reaching

remission, the Hodges-Lehmann estimator of the “location shift” between each dose group and placebo will be presented. The asymptotic (Moses) 95% confidence limits for the location shift will also be presented. The cumulative portion of the time-to-remission of each treatment group will be determined by Kaplan-Meier estimates. The time-to-remission will be analyzed using Cox proportional hazards model with treatment and diabetes stratum as explanatory variables. The following SAS code was used for the analyses of proportional hazards models:

```
proc phreg;  
  Model TIME*CENSOR(0) = TREATMENT DIABSTAT / risklimits;  
run;
```

Subjects who discontinue from the study before remission and subjects who complete the study without reaching remission will be assigned a TTR equal to the larger of the following two quantities:

- (Maximum TTR in days observed for all subjects in the study + 1 day) / 7;
- (Time to censoring (last ALT assessment during the treatment period) + 2 days) / 7.

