Efficacy:	
The primary endpoint of this study is the safety and potential efficacy of two dose levels of JKB-121 (5 mg twice daily and 10 mg twice daily) in reducing liver fat compared to placebo.
 
The secondary endpoint of the study is the time to remission (TTR) is defined as time in weeks from randomization to liver aminotransferase remission as defined as two consecutive ALT values within normal range (< 20 U/L for women and < 30 U/L for men) or a 20% reduction from the baseline during study period. A Cox proportional hazard model will be used to compare the TTR duration between treatment arms.
 
Median duration of TTR and the hazard ratio with 95% confidence limits will be estimated using Kaplan-Meier survival methodology. TTR from randomization will be compared using estimates from the Kaplan-Meier survival curves. A detailed comparison of the treatment effects will be analyzed by fitting a Cox proportional hazard model with baseline variables as covariates to assess the benefit-risk ratio.

Safety:	
The primary safety endpoints will be the rates of patients who experience (1) one or more AEs; (2) SAEs; and (3) AEs leading to discontinuation of study medication. Treatment effect will be explored by inspection of observed means or rates for the dose groups within each treatment regimen. Other safety parameters such as laboratory test, vital signs, and other safety related variables will be summarized regarding each scheduled visit. Shift tables will be presented for laboratory values based on the reference laboratory normal ranges.

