8.1. Subject Inclusion Criteria

Subjects must meet all of the following inclusion criteria to be eligible for enrollment into the study:

1. Age \geq 18 years
2. Provision of written informed consent
3. Biopsy-proven NASH within 12 months prior to randomization as reviewed by central pathologist with:
 - NASH activity score (NAS) of 4 or more
 - 10% or more macrovesicular steatosis
 - cytologic ballooning score of at least 1 point
 - hepatic fibrosis of at least 1 point
 - hematoxylin and eosin (H&E) stained slides and/or paraffin block available for independent assessment
4. ALT $>$ 40 U/L for women and $>$ 60 U/L for men at screening and at least once in the previous 12 months.
5. MRI with $>$ 6% hepatic steatosis
6. HbA1c of \leq 9.0
7. Lipid lowering agents (i.e. statins) and allowable antidiabetic treatment (i.e. metformin or sulfonylurea) must be stable at screening and during the study.
8. Agree to use of effective contraceptive measures if female of child bearing potential.

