### **Responder Analysis**

The number and percentage of responders will be provided by treatment group. A subject who had as two consecutive ALT values within normal range during the treatment period will be defined as a responder. Subjects who are not responders and early withdraw will be considered as non-responders. Cochran-Mantel-Haenszel statistics will be provided adjusting for diabetes stratum.

```
*****  
Note:  
  TREATMENT = 0, (placebo), 1 (JKB-121 5 mg), 2 (JKB-121 10 mg)  
  DIABSTAT = nondiabetic, diabetic  
  RESPONDER: Y/N responder  
  COUNT: number of subjects  
*****;  
proc freq data=ALT;  
  tables DIABSTAT*TREATMENT*RESPONDER / cmh;  
  weight COUNT;  
run;
```

Sensitivity analyses will be conducted using subjects who complete the study.

Similar summaries and analyses will be provided for:

- Subjects whose ALT level at each scheduled visit during the treatment period is within normal range.
- Subjects whose ALT level is within normal range at any time within the following time intervals which will be derived using actual study days:
  - a. Baseline to Week 12

b. Week 12 to Week 24

- Subjects achieving a 20% reduction from baseline at any time during the treatment period.

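### Under the <20/<30 U/L definition, the time-to-remission Cox model does not give a usable comparison of each dose with placebo, whether treatment is fitted as a factor or as the SAS code is printed

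*SAP*

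**What the plan says.** Entry (protocol 8.1) requires "ALT $>$ 40 U/L for women and $>$ 60 U/L for men at screening". In SAP 6.9.2.1, remission is "two consecutive ALT values within normal range during the treatment period (i.e. excluding Week 28 follow-up visit"). The first normal range is "<20 U/L for women and <30 U/L for men". A second range, below 40 U/L for both sexes, is also used: "All TTR and responder analyses described below will be repeated for both ALT normal range definitions".

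For the model the SAP says: "The time-to-remission will be analyzed using Cox proportional hazards model with treatment and diabetes stratum as explanatory variables". Protocol 13.4.1.2 says that treatment and diabetes status enter as factors. The PHREG code printed in the SAP lists TREATMENT and DIABSTAT with the `risklimits` option and has no CLASS statement. The GLM and MIXED code elsewhere in the SAP does have one. TREATMENT is coded 0, 1, 2 wherever the SAP states a coding; the PHREG block itself states none.

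The same section plans Kaplan-Meier curves and, among subjects who reach remission, a Hodges-Lehmann shift between each dose group and placebo. For the responder analysis of the same event, "Cochran-Mantel-Haenszel statistics will be provided adjusting for diabetes stratum". Neither document gives an expected remission rate, says whether inference uses the Wald, score or likelihood-ratio test, or says what to do if an arm has no remissions.

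**The concern.** Remission is hard to reach from the entry ALT, and the arms are small. A Cox model that compares each dose with an arm without events has no finite hazard ratio, and its Wald test carries no information. That is the pattern one would hope to see with an effective drug: remissions on drug and none on placebo. If it occurs, a named secondary endpoint has no reportable estimate, and the team must choose another test after seeing the data. The printed code would hide the problem by answering a different question.

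**Working it through.** **1. Size of the fall required.** Remission limit divided by entry limit:
- <20/<30 definition: 20/40 = 0.50 in women and 30/60 = 0.50 in men, so a fall of more than 50% in both sexes, on two consecutive visits.
- <40 definition: 40/40 = 1.00 in women (almost no fall needed) and 40/60 = 0.67 in men (about a 33% fall).

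**2. Probability of no placebo remission.** If each placebo subject remits with probability p, then P(none of 20) = (1 − p)^20. The plan states no p.

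| p | P(none of 20) |
|---|---|
| 1% | 0.82 |
| 3% | 0.54 |
| 5% | 0.36 |
| 10% | 0.12 |

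The probability exceeds one half when p < 1 − 0.5^(1/20) = 3.4%.

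To bound p, ALT was simulated at screening, Day 1 and the seven treatment visits (Weeks 2, 4, 8, 12, 16, 20, 24), giving six consecutive treatment pairs. From the documents: SD 40 and correlation 0.25 (SAP 6.1), the entry limits and the 250 U/L ceiling. Assumed: mean 70 to 100 U/L, correlation up to 0.75, half women, no improvement on placebo.

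| Definition | Log-normal ALT | Normal ALT |
|---|---|---|
| <20/<30 U/L | 0.74 to 1.00 | 0.18 to 0.89 |
| <40 U/L | 0.02 to 0.93 | 0.01 to 0.63 |

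The 0.74 moves between about 0.67 and 0.77 with modelling details such as the sex mix.

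**3. Treatment as a factor, placebo as reference.** Leave diabetes aside. A remission on dose k contributes exp(b_k) / [n_P + n_5·exp(b_5) + n_10·exp(b_10)] to the partial likelihood, where the n are the numbers at risk. If placebo has no remissions, n_P appears only in denominators. Adding c to both coefficients is the same as replacing n_P by n_P·exp(−c), so the likelihood rises for every increase in c and has no finite maximum.

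Example with 0/6/8 remissions (placebo/5 mg/10 mg, 20 per arm): the fit stops at log hazard ratios of about 16.6 and 16.9 with SE about 1552. Wald z = 16.6/1552 = 0.011 and 16.9/1552 = 0.011, so p = 0.991 for both doses. The two-degree-of-freedom likelihood-ratio p is 0.0014. Unadjusted Fisher p is 0.020 (5 mg) and 0.003 (10 mg).

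Among simulated trials with no placebo remission, with assumed true rates of 1%/15%/30% or 1%/30%/30%, the factor-coded Wald test for 10 mg against placebo rejected in 0% and the likelihood-ratio test in 90% and 98%.

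**4. The code as printed.** Without CLASS, a numeric 0/1/2 TREATMENT is one linear term, which stays finite as long as the 5 mg arm has remissions.

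| Remissions | Hazard ratio per step (95% CI) | Wald p |
|---|---|---|
| 0/6/8 | 2.86 (1.30 to 6.33) | 0.009 |
| 0/3/6 | 3.67 (1.21 to 11.18) | about 0.02 |
| 0/6/0 | 1.00 (0.38 to 2.62) | 1.0 |
| 0/0/6 | diverges | 0.996 |

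The 10 mg ratio is forced to be the square of the 5 mg ratio (2.86² = 8.2 in the first row), so neither dose has its own estimate. In the third row, six remissions of 20 against none give Fisher p = 0.020, but the trend model sees nothing.

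**5. Hodges-Lehmann shift.** It compares times among remitters. With no placebo remitters there is nothing to compare, whichever way the Cox model is coded.

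**The case against.** Several stronger readings are tempting, and the documents do not support them.

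- **That placebo will usually have no remissions.** No rate is stated. All arms receive weight, diet and exercise counselling, ALT can fall after screening, and with normally distributed ALT the probability can be as low as 0.18. Under the <40 U/L repeat, placebo remissions are often likely.
- **That the printed code returns an infinite hazard ratio.** With 0/1/2 coding it generally does not. In simulated trials with no placebo remission, it rejected in 62% to 89% across the assumed scenarios.
- **That the SAP bases inference on the Wald test.** Only `risklimits` points that way, through its default limits; no test is named.
- **That the protocol's median TTR cannot be estimated.** The synopsis plans one ("Median duration of TTR and the hazard ratio with 95% confidence limits will be estimated using Kaplan-Meier survival methodology"), but its definition also accepts a 20% reduction from baseline, which is far easier to reach. The SAP plans no median, and a median not reached is ordinary reporting.
- **That the Cox and CMH results will contradict each other.** The CMH as coded is a stratified test on a three-level treatment table, so p-values from simple two-arm tables are not planned outputs. Responder percentages and Kaplan-Meier curves would still show remissions confined to the drug arms.

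It is also fair to say that the illustrations need a strong effect. A 30% ALT fall gave only 0.1% to 12% remission in simulation, and at 12% the chance of five or more remissions among 20 is about 8%. With few remissions information is low, and no penalty restores it. But divergence does not need many: one remission on drug and none on placebo is enough.

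These objections limit the point to the <20/<30 U/L definition and make it conditional. They do not supply a reading of the plan that gives a sound estimate for each dose against placebo.

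**Conclusion.** The point holds for the <20/<30 U/L definition. Fitted as the protocol describes, the model has no finite hazard ratio and no usable Wald test for either dose if placebo has no remissions. Fitted as printed, it gives a single trend that can miss a non-monotone effect completely. The documents provide no fallback for either case.

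How likely the first failure is depends on the unstated placebo rate: more likely than not below 3.4% per subject, about 0.74 to 1.00 under log-normal ALT and 0.18 to 0.89 under normal ALT, with the assumptions above. The second weakness does not depend on that rate; it requires only that TREATMENT is numeric 0/1/2 in the PHREG data set, as in the SAP's other code. The consequence is confined to a secondary endpoint in a study that describes itself as exploratory.

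**What to change.** In SAP 6.9.2.1, before unblinding:

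1. Add a CLASS statement to the PHREG code for TREATMENT (placebo as reference) and DIABSTAT. If DIABSTAT is stored as text, the code will not run without it.
2. Add FIRTH and RISKLIMITS=PL, and take each dose-versus-placebo p-value from the penalised likelihood ratio, not the Wald statistic. CLASS alone would expose the divergence; FIRTH alone would leave a dose trend. As a two-arm illustration, 5 of 20 against 0 of 20 gives Firth p = 0.020 with profile limits of 1.4 to about 1600: very wide, but finite below and above.
3. Report the proportion in remission by Week 24 in each arm with an exact 95% interval, alongside the Kaplan-Meier curves.
4. State that the Hodges-Lehmann shift is given only when both groups compared have remitters.

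Replacing the CMH with an exact stratified test is optional. The cost is SAP text and a few SAS options, with slight shrinkage of the hazard ratio. No new data are needed, and the same code works if placebo does have remissions, so the change does not depend on the assumed rate.

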5.2.2 Secondary Endpoint(s)

The secondary endpoint of the study is time to remission (TTR). TTR is defined as time in weeks from randomization to liver function remission as defined as two consecutive ALT values within normal range (< 20 U/mL for woman and < 30 U/L for men) or 20% reduction from the baseline during study period.

- TTR rate in ALT at the end of the treatment period.
- Assess the pharmacokinetic profile of JKB-121 in NASH

- Change on metabolic markers associated with NASH
- Change in liver enzymes (serum ALT) over 24 weeks.
- Change of NASH related biomarkers such as adiponectin, leptin, ghrelin, TNF-alpha, TGF-beta, hyaluronic acid and MMP-2.

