13.4.1.2. Secondary Efficacy Endpoint

The secondary endpoints of this study are:

- Time to remission (TTR) is defined as time, in weeks, from randomization to liver function remission as defined as two consecutive ALT values within normal range (< 40 IU/mL) during study period. The Cox proportional hazard model with treatment and diabetes status as factors, will be used.
 - ALT changes from baseline. The statistical analysis will be the same as the one used for the primary efficacy endpoint
 - Changes in metabolic markers and NASH related biomarkers

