## 6.9 Efficacy Analysis

### 6.9.1 Primary Efficacy Endpoint

The change from baseline at Week 24 of the percentage fat content of the liver measured by MRI will be analyzed by analysis of covariance (ANCOVA) in the Full Analysis Set Population with treatment group and diabetes stratum as factors and baseline MRI value as a covariate. The comparisons will be (1) between the response of the JKB-121 5 mg group and the response of the Placebo group and (2) between the response of the JKB-121 10 mg group and the response of the Placebo group. The least-squares means, standard errors, and 95% confidence intervals for each treatment group and for each comparison will be provided. The two-sided p-values testing for significance within treatment group change from baseline and comparisons between treatment groups will be presented. No multiple comparisons techniques will be applied. The sample SAS code can be found below:

```
*****
Note:
  TREATMENT = 0, (placebo), 1 (JKB-121 5 mg), 2 (JKB-121 10 mg)
  DIABSTAT = nondiabetic, diabetic
  BASE: baseline percentage fat content of the liver measured by MRI
  CHG: change from baseline to Week 24 in the percentage fat content of
       the liver measured by MRI
*****;
proc glm data=MRI;
  class TREATMENT DIABSTAT;
  model CHG = TREATMENT DIABSTAT BASE / ss1 ss3;
  means TREATMENT;
  lsmeans TREATMENT / cov stderr pdiff cl;
  estimate "JKB-121 5 mg : Placebo" TREATMENT -1 1 0;
  estimate "JKB-121 10 mg : Placebo" TREATMENT -1 0 1;
run;
```

The data and model residuals will be inspected for normality and homogeneity of variance, and a logarithmic transformation will be applied if necessary.

To handle missing results such as due to early termination, multiple imputation will be performed. The detailed steps are specified below.

Step 1: Prepare the data for multiple imputation. Since there is only one intermediate visit (Week 12) for MRI collection, the missing pattern would be monotone if endpoint values are not available.

Step 2: PROC MI would be used to impute the missing MRI values. The treatment, diabetes stratum, and MRI values at baseline and all available post-baseline visits would be included. The SAS code can be found as below:

```
PROC MI data=MRI out=MI_OUT nimpute=1000 seed=12345 minimum=0;  
  var TREATMENT DIABSTAT BASE WEEK12 WEEK24;  
  mcmc initial=em prior=jeffreys nbiter=200 niter=500 chain=single;  
run;
```

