### 6.9.2.2 Liver Function

The same descriptive statistics, ANCOVA model, and multiple imputation as the primary efficacy endpoint will be applied to serum aspartate aminotransferase (AST), ALT, and gamma-glutamyl transpeptidase (GGT) at each scheduled visit for the Full Analysis Set Population and the mITT Population.

As a sensitivity analysis, the change from baseline in AST, ALT, and GGT will be analyzed using a mixed-model repeated-measures (MMRM) ANCOVA model for the Full Analysis Set Population, implemented using SAS® Proc Mixed. The factors in the model will be diabetes stratum, treatment group, baseline value, visit, and the treatment group by visit interactions. An unstructured covariance matrix will be used (TYPE=UN). No imputation will be performed. The sample SAS code can be found below:

```
*****
Note:
  USUBJID = unique subject identifier
  TREATMENT = 0, (placebo), 1 (JKB-121 5 mg), 2 (JKB-121 10 mg)
  DIABSTAT = nondiabetic, diabetic
  VISIT = visit
  BASE = baseline value
  CHG = change from baseline to the specified visit
*****;
proc mixed;
  class USUBJID DIABSTAT TREATMENT BASE VISIT;
  model CHG = DIABSTAT TREATMENT BASE VISIT TREATMENT*VISIT;
  Repeated VISIT / TYPE=UN sub=USUBJID;
  lsmeans VISIT*TREATMENT / cl pdiff slice=VISIT;
run;
```

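### The Cox code printed for time to remission has no CLASS statement, so as written it cannot give a separate hazard ratio for each dose against placebo

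*SAP*

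**What the plan says.** The protocol synopsis, under Efficacy, states: "A Cox proportional hazard model will be used to compare the TTR duration between treatment arms". Protocol 13.4.1.2 is more specific: "The Cox proportional hazard model with treatment and diabetes status as factors, will be used". Protocol 5.2.2 names TTR as the secondary endpoint.

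SAP 6.9.2.1 (Time to Remission) names treatment and diabetes stratum as the explanatory variables and then prints a PHREG step with the single model line "Model TIME*CENSOR(0) = TREATMENT DIABSTAT / risklimits". The step has no CLASS statement and no note on how the variables are coded. SAP 6.9.2.1 also says that the TTR analyses are repeated for two definitions of the normal ALT range.

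Elsewhere the SAP handles the same variables differently. The GLM code in 6.9.1 has "class TREATMENT DIABSTAT", and the MIXED code in 6.9.2.2 has "class USUBJID DIABSTAT TREATMENT BASE VISIT". The coding notes beside the GLM, FREQ and MIXED code give treatment as 0 for placebo, 1 for 5 mg and 2 for 10 mg. They show the diabetes variable as "DIABSTAT = nondiabetic, diabetic".

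**The concern.** A model term is a factor in PHREG only if it is declared in a CLASS statement. Without that, a numeric treatment variable is fitted as a continuous score, and a text variable is not accepted. The printed code therefore does not carry out what Protocol 13.4.1.2 specifies, whichever way the data are stored.

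At stake is whether each dose is compared with placebo on TTR without assuming a shape for the dose response. With three arms, a continuous score assumes that each dose step multiplies the hazard of remission by the same amount. A plateau, or an effect at one dose only, does not fit that assumption.

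**Working it through.** The documents give no hazard ratio, event count or power for TTR, so there is no stated figure to reproduce. The check is structural, followed by an illustration.

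**Inputs.** Model line: SAP 6.9.2.1. Treatment coding 0/1/2 and the diabetes labels: code notes in SAP 6.9.1, 6.9.2.1 (Responder Analysis) and 6.9.2.2. Requirement for factors: Protocol 13.4.1.2.

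**Case (a): diabetes status stored as text.** This is how the code notes show it. PHREG does not accept a text variable in the model unless it is in CLASS, so the step stops. No wrong result arises, but the code must be changed outside the plan.

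**Case (b): both variables numeric.** The PROC MI step in SAP 6.9.1 lists both variables in its VAR statement, uses the MCMC method and has no CLASS. It therefore needs numeric variables, so this case is plausible too. Let x be treatment (0, 1, 2) and z diabetes status.

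- As printed: h(t) = h0(t)·exp(b·x + g·z).
  - HR(5 mg vs placebo) = exp(b).
  - HR(10 mg vs placebo) = exp(2b) = [exp(b)]².
- With CLASS: h(t) = h0(t)·exp(b1·[x=1] + b2·[x=2] + g·z).
  - HR(5 mg vs placebo) = exp(b1).
  - HR(10 mg vs placebo) = exp(b2), with b1 and b2 free.

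The printed model is the factor model with the constraint b2 = 2·b1. It has one treatment coefficient where two are needed. The two-level diabetes variable loses nothing by being numeric; only treatment is affected.

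**Illustration.** The remission rates are assumptions. Remission times were drawn at random from the visits at Weeks 2 to 20, non-remitters were censored at the time the SAP assigns, and ties were handled by Breslow's method. With 2,000 per arm, to show the systematic difference:

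| Remission: placebo / 5 mg / 10 mg | As printed: HR 5 mg, 10 mg | With CLASS: HR 5 mg, 10 mg |
|---|---|---|
| 20 / 50 / 20% | 1.00, 1.00 | 2.97, 1.00 |
| 20 / 40 / 40% | 1.42, 2.01 | 2.22, 2.21 |
| 20 / 30 / 50% | 1.73, 3.00 | 1.58, 2.93 |

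The printed model's 10 mg column is the square of its 5 mg column (1.42² ≈ 2.0; 1.73² ≈ 3.0). When the true pattern is close to log-linear, as in the third row, little is lost.

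At the planned 20 per arm, with rates of 20/50/20%, one data set gave a printed per-step ratio of 1.02 (95% CI 0.59 to 1.77). The factor model gave 3.13 (0.98 to 9.98) for 5 mg and 1.05 (0.26 to 4.20) for 10 mg. Even the correct model is very imprecise.

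**Dependence on the assumed rates.** Separate simulations at 20 per arm assumed an effect at 10 mg only and 20% dropout in each arm. They counted how often the single treatment ratio's 95% CI excluded 1, which a reader could mistake for a 5 mg effect.

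| Per-visit remission hazard: other arms, 10 mg | CI excludes 1 |
|---|---|
| 0.06, 0.12 | 23% of trials |
| 0.02, 0.04 | about 5% |
| 0.01, 0.02 | below 1% |

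At the two lower pairs, many trials have too few remissions for the models to converge. Rare remission is credible. Entry requires ALT above 40 U/L (women) or 60 U/L (men), and the first remission range is below 20 or 30 U/L. No single error rate should be quoted.

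**The case against.** **The code would be caught.** The notes show diabetes status as text, so the step would fail and a programmer would add CLASS. If it did run, the output would have one treatment row and no row for either dose, which would be noticed when tables by arm are filled. SAP 7.1 also requires program validation. This reduces the practical risk. It does not make the printed code right, and the PROC MI step means that numeric storage cannot be ruled out. That step does not prove it either, since the PHREG block names no data set.

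**The protocol does not promise dose-versus-placebo hazard ratios.** The synopsis speaks of the hazard ratio in the singular, and Protocol 13.2.3 uses Cox only where beneficial. It is true that the two ratios are inferred. The inference is sound: Protocol 13.4.1.2 says without condition that the model will be used with treatment as a factor, and the synopsis has it compare arms. SAP 6.9.2.1 itself estimates the Hodges-Lehmann shift for each dose against placebo. A trend model could be defended, but neither document specifies one.

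**Other outputs show the dose pattern.** Kaplan-Meier estimates, the Hodges-Lehmann shifts (remitters only) and responder percentages are given by arm. This stands, and it limits the harm.

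**Stronger readings.** A reader might infer that the dose recommendation would be misled. The documents do not support this: they set no rule linking the Cox result to the choice of dose. A reader might also infer that non-remitters could be counted as events, because the SAP assigns them a time without stating their CENSOR value. The model line already makes 0 the censored value, and the rule for assigned times refers to a time to censoring. This is an unstated detail, not an error.

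**Conclusion.** The point holds as a minor code correction. As printed, the PHREG step either fails to run or fits one per-step hazard ratio that ties the 10 mg effect to the square of the 5 mg effect. In neither case does it deliver the factor model that Protocol 13.4.1.2 requires.

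The structural result rests on the 0/1/2 coding in the SAP's other notes and on no assumed rates. The numerical examples do rest on assumed rates, and on a reader converting the single ratio into dose-specific ones. They show the direction of the problem, not its likely size in this trial.

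The effect is confined to a secondary analysis in a trial that the SAP describes as exploratory. The primary MRI analysis is untouched. It would be too strong to say that TTR results will be biased: in the text case there is no bias, and in the numeric case the size depends on the unknown dose pattern and remission rate.

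**What to change.** Before database lock, add to the PHREG code in SAP 6.9.2.1:

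`class TREATMENT(ref='0') DIABSTAT / param=ref;`

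State that the hazard ratio with 95% CI will be reported for 5 mg versus placebo and for 10 mg versus placebo, under both ALT normal-range definitions. Add a coding note like those beside the other SAP code. One line in that note can confirm that non-remitters carry CENSOR = 0.

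The cost is one line of code and two or three sentences of SAP text. No new data and no additional analysis are needed.
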